7.5 Number of CTP Sites

Two HIV outpatient clinics will serve as CTPs for this pilot study.

7.6 CTP Characteristics

HIV clinics will be selected on the basis of the following characteristics:

- 1) Provide HIV primary care.
- 2) Have a sufficient population of potential participants to achieve study enrollment goals.
- 3) Have providers willing to be trained in use of XR-NTX for management of opioid or alcohol use disorders.
- 4) Have prior experience participating in research/clinical studies.
- 5) Capable of prescribing ART to all participants, regardless of CD4 count.
- 6) Offer on-site addiction counseling services as part of usual care.

7.7 Rationale for CTP Selection

We will use the same site selection criteria for the pilot study as is planned for the multisite study. Sites will be selected for participation that have an adequate number of HIV-infected participants with untreated opioid use and/or untreated alcohol use disorders. In order to achieve target enrollment for this study, which is approximately 25 participants per site over 12 months of enrollment, we expect that participating HIV clinics will need to see $\geq 1,000$ unduplicated HIV-infected potential participants per year. This number is based on estimates of the percent of HIV-infected patients in 17 HIV clinics that were informally queried regarding participant availability (Appendix C), and experience of CHOICES investigators in enrolling subjects in the BHIVES study (Altice, Bruce et al. 2011). We have also included site selection criteria that attempt to limit site variability in treatment effects (e.g., capacity for prescribing ART regardless of CD4 count, presence of on-site addiction counseling services).

7.8 Collaboration with CTSA for Site Recruitment

CTP recruitment will explore opportunities to partner with the NIH-funded Clinical and Translational Science Award (CTSA) consortium. CTSA institutions "work to transform local, regional, and national environment to increase the efficiency and speed of clinical and translational research" (CTSA Consortium 2012). Potential opportunities for collaboration between CTN-0055 and affiliated CTSA include CTSA assistance with community based recruitment and/or some aspects of study implementation.

8.0 OUTCOME MEASURES

8.1 Primary Outcome Measures

Primary outcome variables for the CHOICES pilot study are:

- 1) HIV provider willingness to prescribe XR-NTX (Aim 1): HIV provider willingness to prescribe opioid antagonist treatment will be assessed with survey measures adapted from the Medical Opinion Survey (MOS) during the study start-up period (mean; survey data).
- 2) Patient acceptance of opioid antagonist therapy (Aim 2): HIV-infected patient acceptance of opioid antagonist treatment will be assessed with measures adapted from the Medical Opinion Survey (MOS), administered during participant recruitment. Patients will be asked whether they are willing to participate in a trial of XR-NTX vs. TAU (binary; survey data).
- 3) Rate of participant recruitment into trial (Aim 3): This will be used to estimate the speed at which a multisite trial could enroll participants. The number of participants randomized will be assessed on a monthly basis until either 50 participants have enrolled, or 12 months of recruitment have elapsed, whichever comes first (rate; randomization data).
- 4) Treatment initiation (Aim 4A): Treatment initiation is defined as receipt of at least one dose of study medication for those randomized to XR-NTX within 4 weeks of randomization. For those randomized to TAU, treatment initiation will be defined as receiving at least one dose of medication-assisted therapy other than XR-NTX (e.g., buprenorphine for opioid use disorder, disulfiram for alcohol use disorder), or attendance on at least 1 day of non- medication-assisted therapies (e.g., 12-step groups, outpatient rehab referral, etc.) within 4 weeks of randomization. For the TAU group, treatment initiation will be assessed with weekly phone calls from research staff until treatment is initiated or 4 weeks from date of randomization have elapsed, as which point a participant will be considered to have failed treatment initiation (binary; chart review and self-report).
- 5) Retention on treatment (Aim 4B): Retention on treatment is defined as the percent of assigned treatment received over 16 weeks after treatment initiation. Only participants who initiate treatment (as defined in Aim 4A) will be assessed for retention on treatment. Retention will be assessed by the study clinician at 4, 8, 12, and 16 weeks following treatment initiation. For those randomized to XR-NTX, retention on treatment is defined as the mean percent of expected XR-NTX doses received (25%, 50%, 75%, or 100% of 4 possible doses). For those randomized to TAU, study clinicians will estimate the percent of recommended treatment a participant received in the past 4 weeks at weeks 4, 8, 12, and 16. Retention on treatment for TAU is defined as the mean percent of recommended TAU treatment received (1-100% possible range), as estimated by the study clinician (percent; chart review and self-report).

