we will survey HIV-infected patients regarding attitudes toward opioid antagonist therapy (Aim 2), track rate of participant recruitment (Aim 3), and randomize those who have untreated opioid and/or alcohol use disorders to receive XR-NTX vs. TAU (Aim 4). Participants will attend study visits every 4 weeks for 16 weeks. Treatment initiation will be assessed at 4 weeks and retention at 16 weeks (4 XR-NTX injections). Randomization will continue until a maximum of 50 participants or 12 months are reached. Pilot study duration will be a maximum of 17 months (maximum 12 months recruitment + 5 months study participation for those enrolled at the end of the recruitment period). We will assess feasibility of a multi-site trial of XR-NTX vs. TAU by addressing four pilot study specific aims.

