9.3.3.3 Active Treatment with XR-NTX (Treatment Week 0 through Week 16)

Following a negative naloxone challenge, XR-NTX monthly injections will begin. XR-NTX (4cc, ~380mg of naltrexone base) will be administered approximately every four weeks (weeks 0, 4, 8, 12) for a maximum of 4 doses in the form of Vivitrol®, which will be obtained by NIDA or the NIDA contractor for distribution to the sites. XR-NTX will be administered by intramuscular injection to the buttocks (alternating sides monthly) according to the injection preparation and administration procedures specified in the Vivitrol® product package insert. These procedures are designed to minimize the risk of injection site reactions.

9.3.3.4 *Handling of Missed XR-NTX Doses, Lapses, and Relapses*

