The proposal for a phase III randomized trial assumes enrollment of 400 participants from 8 sites in 18 months, implying a recruitment rate of about 2.28 participants per site-month. **Table 17.2.1** explores by simulation the consequences for the precision of various pilot-study-derived estimates of having a pilot study in which per site-month recruitment rate = (1.14, 2.28), number of sites = (1,2), and time period = (12 months, 18 months). **Table 17.2.1** investigates limiting the pilot sample size to 50 participants (n-limited), or limiting the enrollment time to 12 or 18 months (t-limited), or limiting both sample size and recruitment time simultaneously (n- and t-limited). The columns of **Table 17.2.1** headed – “Parameters” depict all the parameter combinations investigated.

5) The notation used in **Table 17.2.1** follows:

- n = pilot study sample size
- t = pilot study recruitment time (months)
- s = number of sites in the pilot study
- rate = recruitment rate (participants per site-month) assumed for both the pilot study and the subsequent phase III randomized trial
- N = randomized trial sample size (assumed to be 400)
- T = randomized trial recruitment time (months). This assumes that the sites in the randomized trial will exhibit the same performance that they did in the pilot study.
- S = number of sites in the randomized trial (this is not actually shown in **Table 17.2.1**, but is assumed to be 8)
- $\hat{T} = \frac{s/n}{S/N} t$, the estimator, derived from the pilot study, of the recruitment time for the subsequent phase III randomized trial
- $p(\text{init})$ = the probability of treatment initiation, which is the chance that a participant who is randomized to one of the two arms within the pilot study will obtain the 1st dose of the treatment. There is one $p(\text{init})$ calculated for each of the two arms.
- $p(\text{ret})$ = the probability of retention, which is the chance that a pilot-study participant who has obtained the 1st dose will still be on treatment at 4 months. There is one $p(\text{ret})$ calculated for each of the two arms.

6) The columns of **Table 17.2.1** headed “Outcomes (Percentiles)” show the consequences for various outcomes, given the parameters controlling the pilot study. Their meanings follow:

- 20% n = the 20th percentile of the sample size of the pilot study. The pilot study will very likely recruit at least this many participants

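### Aim 4B credits XR-NTX at the start of each 4-week interval but TAU by look-back through week 16, so identical dropout favours XR-NTX by an amount that depends on how TAU is rated

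*Protocol*

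**What the plan says.** Section 5.1 (Objective 4B) sets out to compare 16-week retention between XR-NTX and TAU. Sections 8.1 and 17.1 restrict the measure to participants who initiated treatment and give each arm its own scoring rule.

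- **XR-NTX:** "retention on treatment is defined as the mean percent of expected XR-NTX doses received (25%, 50%, 75%, or 100% of 4 possible doses". Section 9.3.3.3 says the drug is "administered approximately every four weeks (weeks 0, 4, 8, 12) for a maximum of 4 doses". The assessment table in section 10.1 shows the same four dose visits and none at week 16.
- **TAU:** "study clinicians will estimate the percent of recommended treatment a participant received in the past 4 weeks at weeks 4, 8, 12, and 16". The score is the "mean percent of recommended TAU treatment received (1-100% possible range), as estimated by the study clinician".

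Two other places describe the same outcome differently. The synopsis (section 2.0) says: "Treatment initiation will be assessed at 4 weeks and retention at 16 weeks (4 XR-NTX injections". The sample-size text under section 17.2 defines p(ret) as "the chance that a pilot-study participant who has obtained the 1st dose will still be on treatment at 4 months", and section 17.3 analyses it as a binomial proportion in each arm. The clock also differs: section 8.1 starts the 16 weeks at treatment initiation, section 17.1 at randomization.

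**The concern.** An injection earns its quarter of the XR-NTX score on the day it is given, at the start of the four weeks it covers. TAU earns credit only afterwards, for what was received during the four weeks just ended. Two cases show the effect:

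- A participant who stops the day after the week-12 visit scores 100% on XR-NTX but loses credit for weeks 12 to 16 on TAU.
- A participant who stops straight after initiation scores 25% on XR-NTX and can fall close to the 1% floor on TAU.

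With the same dropout curve in both arms, XR-NTX therefore comes out ahead whenever there is any dropout. The direction needs no outside assumption. At stake is the reading of a primary outcome: a difference produced partly by the scoring rule could be taken as greater willingness to stay on XR-NTX.

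**Working it through.** **The plan's own figure.** The protocol states no between-arm retention difference. Its only figure for this outcome is the per-arm 95% confidence half-width of 0.22 for p(ret), in the chosen row of Table 17.2.1. It reproduces. Expected recruitment is 2.28 × 2 sites × 12 months = 54.7, with a 20th percentile of 48, or 24 per arm. With 10% attrition before initiation about 21 to 22 remain. The exact binomial half-width near p = 0.5 (assumed) is 0.223 at n = 21 and 0.218 at n = 22.

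**Inputs for the gap.** Let S(t) be the proportion of initiators still on treatment at week t, the same in both arms, with S(0) = 1. The protocol assumes no 16-week rate. As an illustration I use the six-month retention of 53% (XR-NTX) and 38% (placebo) that section 4.2 cites from the placebo-controlled opioid trial. I read six months as 24 weeks and assume a constant hazard and full treatment until stopping.

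- 53%: h = −ln(0.53)/24 = 0.02645 per week. S(4), S(8), S(12), S(16) = 0.900, 0.809, 0.728, 0.655.
- 38%: h = −ln(0.38)/24 = 0.04032 per week. S(4), S(8), S(12), S(16) = 0.851, 0.724, 0.616, 0.525.

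**Formulas.**

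- XR-NTX percent = [1 + S(4) + S(8) + S(12)]/4.
- TAU percent, pro rata = (1 − e^(−16h))/(16h).
- TAU percent, each window all-or-none = [S(4) + S(8) + S(12) + S(16)]/4. The gap is then exactly [1 − S(16)]/4.
- Binary reading: XR-NTX = S(12), because no dose is scheduled later, and TAU = S(16).

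| Scoring | 53% curve: XR-NTX vs TAU (gap) | 38% curve: XR-NTX vs TAU (gap) |
|---|---|---|
| Percent, TAU pro rata | 85.9 vs 81.5 (4.4) | 79.8 vs 73.7 (6.1) |
| Percent, TAU all-or-none | 85.9 vs 77.3 (8.6) | 79.8 vs 67.9 (11.9) |
| Binary, on treatment at 4 months | 72.8 vs 65.5 (7.3) | 61.6 vs 52.5 (9.2) |

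**Sensitivity.**

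- Six months read as 26 weeks: 4.1 and 5.7 pro rata, 8.1 and 11.2 all-or-none, 6.9 and 8.8 binary.
- Section 6.3 says most losses in earlier trials came in the first 16 weeks. If between half and all of the loss falls there, the gap runs from 2.9 to 8.1 points pro rata and 5.9 to 15.5 all-or-none.
- 90% on treatment at week 16: 1.3 pro rata, 2.5 all-or-none, 2.4 binary. 80%: 2.5, 5.0 and 4.6.
- Fourth dose given at week 15: the binary gap is S(15) − S(16) = 1.8 points (53% curve) or 2.2 points (38% curve).

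**Testing possible corrections on the same curves.**

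- Both arms yes/no at week 12: S(12) − S(12) = 0.
- Both arms yes/no at weeks 4, 8 and 12, averaged: 81.2 vs 81.2 and 73.1 vs 73.1, gap 0.
- Injections at weeks 4, 8 and 12 against pro rata TAU look-back over weeks 0 to 12: 81.2 vs 85.7 and 73.1 vs 79.3. The gap is −4.5 and −6.2 points, so the bias is reversed rather than removed.

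**The case against.** The strongest reply is that the depot really does treat through week 16. Section 2.0 gives an injection a 28-day duration, and section 8.1 frames retention as the share of assigned treatment received. On that reading, 100% after the week-12 dose is correct, and assured adherence is the point of the product. This stands as a statement about drug exposure. It does not make the difference a comparison of staying in treatment, because TAU participants must keep attending or taking medication to earn the same credit, and the protocol does not say that exposure is what it means to compare.

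A second reply is that section 9.3.3.4 lets participants who miss a dose but remain abstinent restart up to three weeks late. A reader might infer that nothing after week 12 can alter an XR-NTX score. That is not so: a fourth dose may fall as late as week 15, and for those participants the gap is much smaller. Doses given on schedule leave it intact.

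Third, section 17.3 estimates each arm separately with no between-arm test, and the accepted per-arm precision (±0.22) is wider than the gap. Both are true. But the ±0.22 is sampling error, whereas the gap is systematic and would not shrink with more participants, and Objective 4B does say compare.

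Fourth, the 53% and 38% come from an opioid-only trial after inpatient detoxification, and neither is a TAU rate. That stands too, which is why the size is a range.

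**Conclusion.** The mismatch is real and its direction follows from the protocol's text. Its size is not fixed by the protocol. Under a constant hazard through the cited six-month rates it is about 4 to 6 points (TAU pro rata), 9 to 12 (TAU all-or-none) or 7 to 9 (binary). It is about 1 to 5 points if 80 to 90% are still on treatment at week 16, and smaller for those whose fourth dose is late.

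Three stronger readings are not supported:

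- A single 7-to-9-point bias on Aim 4B. That range belongs to the binary p(ret) wording, not to the percent definition in section 8.1.
- That the whole gap is artefact. Part of it is depot coverage of weeks 12 to 16, so the difference as defined should be read as drug exposure, not as willingness to stay.
- That the difference will distort the phase III design, or that section 6.3 is wrong. The protocol assumes 400 participants for the later trial, describes viral suppression as the primary outcome of a multisite trial, and nowhere says the retention difference feeds its design. Section 6.3 says only that 16 weeks should suffice to assess initial retention.

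The point merits correction because the outcome is primary and the remedy is cheap.

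**What to change.** For the between-arm comparison, score both arms yes/no at the same decision point. XR-NTX counts as retained if the fourth injection was received, and TAU if treatment is still being received at the week-12 visit, with the same scoring allowance for lateness in both arms. Keep the 16-week percent-received measure as a per-arm description of exposure.

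If a percent-scale comparison is wanted, score TAU yes/no at weeks 4, 8 and 12 as well. Do not set the week 4, 8 and 12 injections against pro rata TAU look-back ratings.

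Reconcile the wording of 16-week retention and p(ret) in sections 2.0, 8.1, 17.1 and the sample-size text under 17.2, including whether the clock starts at initiation or randomization.

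No new visits are needed. The Treatment Services Review and Medication Assisted Treatment forms are already collected at week 12 (section 10.1). They look back 28 days, so the text must state how current receipt at the visit is decided. The costs are wording, and the TAU rating for weeks 12 to 16 leaves the matched comparison, which should then be labelled as retention to the week-12 decision.

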8.2 Secondary Outcome Measures

1) HIV outcomes:

- a) HIV-1 RNA viral suppression (plasma HIV-1 RNA pcr < 200 copies/mL) at 16 weeks compared with screening (binary, laboratory assay).
- b) Change in CD4 count at 16 weeks following treatment initiation compared with screening (count; laboratory measurement).

2) Substance Use:

- a) Change in 30 day opioid abstinence (by Addiction Severity Index (ASI)-lite self-report, Time-Line Follow-Back (TLFB) and urine drug screen (UDS) confirmation) in the final 30 days of the 16 week trial compared to screening (binary; laboratory data and self-report).
- b) Change in past 30-day alcohol and other drug use by ASI-lite, TLFB and UDS at week 16 visit, compared to screening (binary; laboratory data and self-report).

3) Engagement in HIV Care:

- a) Change in the proportion of participants prescribed ART within 16 weeks following randomization, compared to baseline (binary; medical record abstraction).
- b) Proportion of participants taking 100% of prescribed ART doses in the past 3 days at 16 weeks for those prescribed ART at any point during the 16 week trial (proportion; self-reported ACTG adherence measure).
- c) Number of HIV primary care visits at 16 weeks (count, chart abstraction).

4) Participant safety:

- a) Change in liver enzymes between screening and week 16 visit (laboratory assay).
- b) Any fatal and non-fatal opioid overdose between screening and week 16 (binary; medical record abstraction and self-report).
- c) Change in Concise Health Risk Tracking score between screening and week 16 visit (continuous; self-report).
- d) Proportion of participants assigned to XR-NTX who develop precipitated opioid withdrawal.

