Yet little is known about XR-NTX implementation in U.S. office-based settings, and the FDA's decision has been criticized insofar as (1) the FDA "accepted a single trial of injectable naltrexone in Russia, unpublished at the time, as primary evidence of efficacy", and (2) "the study did not adequately assess risk of post-treatment overdose" (Wolfe, Carrieri et al. 2011). Because agonist therapy is prohibited in Russia, these authors question the use of these data to gain approval in the USA where methadone and buprenorphine are widely available. Regardless of the merit of these concerns, the data from the Russian placebo-controlled efficacy trial do not directly address the effectiveness, comparative effectiveness, safety, and costs of XR-NTX in U.S. HIV-infected populations.

Naltrexone for Treatment of Alcohol Use Disorders. Oral naltrexone received FDA approval in 1994 for treatment of alcohol use disorders and systematic reviews support its efficacy compared to placebo (Kranzler and Van Kirk 2001; Bouza, Angeles et al. 2004; Srisurapanont and Jarusuraisin 2005), but its success is limited by suboptimal adherence to daily dosing requirements (Hermos, Young et al. 2004; Kranzler, Stephenson et al. 2008). XR-NTX, which lasts 28 days, has improved response rates in alcohol-dependent patients. In a 6-month, multicenter trial of XR-NTX for alcohol dependence, those randomized to receive 380mg XR-NTX experienced a 25% greater decrease in heavy drinking day event rate compared to placebo (Garbutt, Kranzler et al. 2005), improved quality of life (Pettinati, Gastfriend et al. 2009), and decreased holiday drinking (Lapham, Forman et al. 2009). In a post-hoc analysis limited to those with higher severity alcohol dependence, XR-NTX reduced heavy drinking days by 37% and improved maintenance of abstinence compared with placebo (Pettinati, Silverman et al. 2011). Treatment responses were highest among participants with at least 4 days of voluntary alcohol abstinence prior to their first dose of XR-NTX (Garbutt, Kranzler et al. 2005; O'Malley, Garbutt et al. 2007), and were rapid in onset, with significant reductions in alcohol use observed after only 2 days (Ciraulo, Dong et al. 2008). XR-NTX did not significantly increase counseling or support group participation (Cisler, Silverman et al. 2010).

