The pilot study consists of a two-arm, 16-week, open-label, randomized, pilot trial of XR-NTX vs. TAU for treatment of opioid and alcohol use disorders in HIV-infected patients. Study participants are individuals with HIV infection and alcohol and/or opioid use disorders and who have received patient-centered information about both antagonist and agonist treatment options for alcohol and opioid use disorders. During screening, eligible participants will be surveyed regarding their attitudes about opioid antagonist therapy for opioid and alcohol use disorders (Aim 2). We will track the rate of participant recruitment (i.e., no more than 50 participants over no more than 12 months) to estimate duration of study recruitment required for a multisite study (Aim 3). Eligible patients are randomized in a 1:1 ratio to receive XR-NTX vs. TAU (Aim 4). Participants with both alcohol and opioid use disorders will be categorized by their self-reported substance of choice. XR-NTX (provided as Vivitrol®) will be administered by HIV clinic providers as a monthly intramuscular injection. Study visits will occur every 4 weeks for collection of blood and urine samples, safety, and other assessments. Primary outcomes of treatment initiation within 4 weeks of randomization, and retention at 16 weeks (maximum of 4 XR-NTX injections) and analyzed by intent-to-treat will be assessed. Secondary outcomes assessed at 16 weeks include change in 1) HIV-1 RNA viral suppression, 2) illicit drug and alcohol use, 3) HIV care engagement (receipt of ART, HIV visit adherence, ART adherence), and safety (percent with precipitated withdrawal, overdose, transaminitis).

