7.0 STUDY POPULATION

7.1 Inclusion Criteria

Participating individuals in the provider acceptability survey are HIV providers, defined as any physician, nurse practitioner, or physician assistant who serves as primary HIV provider for HIV- infected patients at least one half day per week.

Individuals participating in the pilot study must:

- 1) Meet DSM-5 criteria for moderate or severe opioid use disorder and/or alcohol use disorder.
- 2) Be willing to be randomized to antagonist-based therapy or TAU for treatment of opioid and/or alcohol use disorders.
- 3) Be HIV-infected as defined by history of positive HIV serology or HIV RNA pcr > 10,000 copies/mL).
- 4) Be willing to establish ongoing HIV care at CTP if not already receiving ongoing care.
- 5) Be willing to initiate ART if not already prescribed ART, regardless of CD4 count.
- 6) Be at least 18 years old.
- 7) Be able to provide written informed consent and HIPAA (if applicable) for medical record abstraction.
- 8) Be able to communicate in English.
- 9) If female, be willing to take measures to avoid becoming pregnant.

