13.2 Urine Ethyl Glucuronide

Urine will be collected for ethyl glucuronide testing at screening, 1 week after induction (Safety Visit), and 4, 8, 12, and 16 weeks (or end-of-medication/end-of-treatment visit if medication or TAU intervention is stopped early) for assessment of secondary outcomes. Ethyl glucuronide is a biomarker of alcohol consumption in the previous 22 to 31 hours and will be used to confirm self-reported alcohol abstinence (Dahl, Stephanson et al. 2002; Wurst and Metzger 2002).

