15.4 Precipitated Withdrawal

For participants assigned to XR-NTX, the study clinician will record the presence or absence of precipitated opioid withdrawal following each XR-NTX injection.

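### Opioid abstinence, alcohol/other drug use and precipitated withdrawal are not tied to the participant's own disorder or exposure, so their estimates depend on a case mix the protocol does not state

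*Protocol*

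**What the plan says.** Protocol 7.1 requires that participants "Meet DSM-5 criteria for moderate or severe opioid use disorder and/or alcohol use disorder", so the sample may hold opioid-only, alcohol-only and dual-disorder participants. No expected split is given.

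- **Withdrawal (4d).** Section 8.2 defines it as the "Proportion of participants assigned to XR-NTX who develop precipitated opioid withdrawal". The same denominator stands in 5.2, 17.2 and 17.5. Under 15.4 the study clinician "will record the presence or absence of precipitated opioid withdrawal following each XR-NTX injection", so the event can be recorded only in someone who was injected. Section 4.2 describes precipitated withdrawal as an effect in people physiologically dependent on opioids.
- **Opioid abstinence (2a).** Sections 5.2, 8.2 and 17.2 set no restriction by disorder. Section 17.5 assigns rank-based methods without restriction or stratification, and 17.6 analyses patients in the arm to which they were randomized.
- **Alcohol and other drugs (2b).** Section 8.2 reads "Change in past 30-day alcohol and other drug use by ASI-lite, TLFB and UDS at week 16 visit, compared to screening" and labels the item binary. Other drug use is not defined. Ethyl glucuronide (EtG) is not named in 2b, although 13.2 says it "will be used to confirm self-reported alcohol abstinence".

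Section 9.2.8 expects the predominant disorder to correlate strongly with primary and secondary outcomes and has it recorded at randomization. Section 6.1 categorizes dual-disorder participants by preferred substance. Section 17 uses neither item. Elsewhere the protocol does set conditional denominators: retention is assessed only in initiators (8.1), and ART adherence only in those prescribed ART (8.2, item 3b).

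**The concern.** Aim 4 Pilot Objective B and section 5.2 make point estimates for the secondary outcomes a product of this pilot, to inform a multi-site trial. An estimate that pools people who can show an effect with people who largely cannot depends on the enrolled mix as well as on the treatment. A planner who reads 4d as the risk for an opioid-dependent person given XR-NTX, or 2a as the effect on opioid use in people with an opioid problem, would take too small a number. In 2b, someone who stops drinking but still has a positive screen for another drug would count as unchanged if the item is scored as one composite.

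**Working it through.** **1. The plan's own figure.** The protocol states no withdrawal rate, disorder mix or substance-use effect. The nearest stated figures are in Table 17.2.1: at 2.28 participants per site-month, two sites, and limits of 50 participants and 12 months, the 20th percentile of n is 48 and the interval half-widths are 0.21 for initiation and 0.22 for retention.

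Poisson recruitment with mean 2.28 × 2 × 12 = 54.72, capped at 50, gives a 20th percentile of 48. With two equal arms, p = 0.5 and exact limits, the simulated 80th-percentile half-width is 0.205 (0.209 at exactly 24 per arm). With 10% attrition before initiation it is 0.223. The row reproduces, and it supplies the planning value of 90% initiation used below.

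**2. Inputs**
- Section 2.0: "Randomization will continue until a maximum of 50 participants or 12 months are reached". With 1:1 allocation (6.1) this is at most 25 per arm.
- i, the share injected: 0.90 (section 17.2); 0.75 is an assumed alternative.
- q, the share with opioid use disorder: not stated, assumed 0.32 to 1. The value 0.32 comes from a cohort of HIV-infected veterans on oral naltrexone cited in 4.1. It is not a forecast for this trial.
- Opioid abstinence among those with opioid use disorder: 50% vs 25%, an assumption for illustration.

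**3. Withdrawal.** Let E events occur among N assigned, all in injected participants with opioid use disorder, with i the same across disorders. The reported proportion is E/N and the proportion among those exposed is E/(N × q × i). Their ratio is 1/(q × i).

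**4. Opioid abstinence.** If alcohol-only participants use no opioids at either time, their change is zero and the pooled risk difference is q × 0.25.

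| q | Withdrawal factor, i = 0.90 | Withdrawal factor, i = 0.75 | Pooled abstinence difference |
|---|---|---|---|
| 1.00 | 1.11 | 1.33 | 0.250 |
| 0.80 | 1.39 | 1.67 | 0.200 |
| 0.67 | 1.66 | 1.99 | 0.168 |
| 0.50 | 2.22 | 2.67 | 0.125 |
| 0.32 | 3.47 | 4.17 | 0.080 |

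The factor reaches 2 only when q × i ≤ 0.50, that is q ≤ 0.50/0.90 = 0.56 at the planned initiation.

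**5. In counts.** One event among 25 assigned is 4.0% (exact 95% CI 0.1 to 20.4). With q = 0.5 and i = 0.9, 25 × 0.5 × 0.9 = 11.25, or about 11 exposed, and the same event is 9.1% (0.2 to 41.3). With no events the upper limit moves from 13.7% to 28.5%.

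**6. Power.** For 50% vs 25% at q = 0.5, power is about 20% with everyone and 24% in the opioid-disorder subset. Both are low, so the effect is on what is estimated, not mainly on power.

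**7. Item 2b.** The urine panel in 13.1 contains no alcohol marker. EtG has its own section (13.2) and its own row in the assessment table, but that row is filed on the UDS form. The data needed for a separate alcohol outcome are therefore collected; the outcome wording does not separate them.

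**The case against.** **The pooled estimates are legitimate.** The all-assigned proportion is a proper intent-to-treat quantity, and Pilot Objective B names a mixed population of patients with alcohol or opioid use disorders. This stands: neither figure is biased for its literal target, and both should be kept. But a mixed-population effect carries over to the next trial only if the mix carries over too, and the protocol does not fix the mix.

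**By-disorder analyses could sit in an SAP.** They could, and none is at hand. But the protocol itself fixes the denominator of 4d in four places and words 2b as a single item.

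**Item 2b may mean one binary per substance.** ASI-Lite has separate drug and alcohol sections and the urine screen reports drugs individually, so this reading is open. The wording still needs to say which is meant.

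**Opioid change in alcohol-only participants need not be zero.** Section 7.1 requires only one moderate or severe disorder, so an alcohol participant may have milder opioid use, and 9.3.3.2 ties the naloxone challenge to recent use and not to diagnosis. This stands. It makes the dilution in the table an upper bound, and a diagnosis-only denominator for withdrawal could miss exposed opioid users.

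A reader might infer two further things that the documents do not support. One is that alcohol use has no laboratory check: 13.2 and the UDS form largely supply the link, so this is a gap in wording. The other is that an any-use alcohol outcome contradicts the cited evidence, because section 4.1 reports that treated patients "experienced a 25% greater decrease in heavy drinking day event rate compared to placebo". The same section also cites better maintenance of abstinence and fewer drinking days.

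**Conclusion.** The point holds as a matter of definition and reporting. None of the three outcomes is tied to the disorder or exposure that makes it informative, and two of them (2a and 4d) move with an unstated mix. At 90% initiation the all-assigned withdrawal figure is about 1.1 to 3.5 times lower than the risk per injected participant with opioid use disorder, for q from 1 down to 0.32. An illustrative 25-point difference in opioid abstinence becomes 12.5 points at q = 0.5 and 8 points at q = 0.32, if alcohol-only participants use no opioids at either time.

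A reader might infer that withdrawal risk is understated two-fold or more. The documents do not support that as a general statement: it needs an opioid-disorder share of about 56% or less at the planned initiation, or lower initiation. With mostly opioid-disorder enrolment the factor is 1.1 to 1.7. These are secondary outcomes that 17.5 calls hypothesis-generating, so the matter is worth correcting but does not threaten the primary aims.

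**What to change.** Amend 5.2, 8.2, 17.2 and 17.5 together:

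- Keep the all-randomized and all-assigned figures.
- **4d:** add precipitated withdrawal per injected participant with opioid use disorder or recent opioid use before injection, and per injection.
- **2a:** also report it in participants with DSM-5 opioid use disorder at screening, including those with both disorders.
- **2b:** split it. Report alcohol use in participants with DSM-5 alcohol use disorder at screening, by TLFB and ASI-Lite, naming EtG as the confirmation already intended in 13.2. Define other drug use and report it separately. The TLFB, missing from 2b in 17.2, should be restored there. Heavy drinking days from the TLFB are optional.

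Take membership for 2a and 2b from the screening DSM-5 Checklist, not from preferred substance, so that dual-disorder participants count in both sets. Because it is fixed before randomization, the between-arm comparisons remain randomized. The added withdrawal figures are descriptive and concern one arm only.

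The Checklist, TLFB, EtG and injection log are already scheduled, so no new data are needed. The cost is fewer participants and wider intervals in each disorder-specific estimate, as the 11-person example shows.
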